7.2 Immunogenicity

Blood samples taken from the subjects throughout the study will undergo three-tiered testing. Initially, they will be screened for AIA. Samples with a result falling above a pre-specified threshold will be deemed 'screened positive', otherwise they will be reported as 'negative'. The samples that were "screened positive" will be subsequently tested in the confirmatory assay and will be reported as either 'negative' or 'confirmed positive'. Finally, if found to be 'confirmed positive', samples will then undergo AIA titer analysis in which the sample is diluted until it crosses the specific cut-point, which allows for semi-quantification. In addition, the confirmed positive samples will be tested for neutralizing activity within the neutralizing assay.

1) Confirmed Positive AIA

A subject is deemed to have confirmed positive AIA at a timepoint if both, the screening assay and the confirmatory assay at that timepoint have a positive result, as described above. A subject can have a confirmed positive AIA at any timepoint, including baseline.

2) Negative AIA

A subject is deemed to have negative AIA at a time point if the screening assay at that time point has a negative result. A subject can have a negative AIA at any time point, including baseline.

3) Newly Confirmed Anti-insulin Neutralizing Antibody (NAb)

A subject is deemed to have developed newly confirmed NAb if the subject has a negative AIA at baseline and a confirmed positive AIA after baseline and up to visit Week 26 and has developed anti-insulin neutralizing antibodies after baseline and up to visit Week 26 at any post-baseline measurements.

4) Newly Confirmed Positive AIA

A subject is deemed to have developed a newly confirmed positive AIA if the subject has a negative AIA at baseline, and a confirmed positive AIA after baseline and up to visit Week 26.

5) Important increase in AIA titers

An important increase in AIA titers is defined for subjects who have a (1) confirmed positive AIA at baseline and (2) a non-missing baseline and post-baseline titer analysis, and the ratio of post-baseline titer to baseline titer is greater than or equal to 4.

6) Treatment-Induced AIA

Treatment-Induced AIA (primary endpoint) is defined as one of the following:

- Newly Confirmed post-baseline positive AIA (in baseline negative)
- Important increase in AIA titers (in baseline positive and with 4-fold increase in titers; post-baseline-to-baseline ratio.)

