11.6.1.2 Methods for Handling Dropouts and Missing Data

Utilizing a "Treatment Policy" strategy, missing data (after using data collected during or after treatment, and assigning data to the appropriate scheduled visit as described above) for the primary endpoint will be imputed as per Table 4. Sites have been trained in the importance of collecting baseline AIA samples. In the rare and unlikely event a site does not collect a baseline AIA sample, imputation rule for missing baseline assessment is included in the table. Unscheduled assessments (e.g. EOT documented at visit Week 26 outside the visit windows for discontinued subjects) up to visit Week 26 will be considered in the overall result but will not be imputed.

Table 4: Imputation Rules for Missing Data in Primary Immunogenicity Analysis

Category	Sample Availability	Imputation	Likely Scenarios
1	All three AIA samples collected and analyzed	
 No imputation 	
 Subjects complete the study. Dropout subjects provide the required AIA samples within the defined visit window.
2	At least one AIA sample missing at Week 12 or Week 26 regardless of baseline sample availability	
 Subject will be counted as 'developing a treatment-induced AIA'. 	
 Dropout subjects who are unable to provide AIA samples in respective visit window. AIA sample missing due to protocol deviations.

Category	Sample Availability	Imputation	Likely Scenarios
3	Baseline sample missing, but both Week 12 and Week 26 samples are collected and analyzed	
 Subject will be counted as 'developing a treatment-induced AIA' if any of Week 12 or Week 26 results are positive. Subject will be counted as 'NOT developing a treatment-induced AIA' if both Week 12 and Week 26 results are negative. 	
 Baseline AIA sample missing due to protocol deviations.

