11.6.2 Secondary Immunogenicity Endpoints

All analyses will include on and after study treatment AIA data up to visit Week 26.

11.6.2.1 Subjects with Negative Anti-Insulin Antibodies at Baseline Who Develop Newly Confirmed Positive Anti-Insulin Antibodies

The percentage of subjects in each treatment group with negative AIA at baseline who develop newly confirmed positive AIA after baseline and up to visit Week 26 will be summarized in proportions. The difference in proportions will be estimated along with the corresponding 90% CI in the subset of SS using a logistic regression model.

Missing data will be imputed as described for the primary endpoint in Table 4.

Sponsor: Gan & Lee Pharmaceuticals, USA Corporation
Protocol no: GL-GLAT2-3002

Statistical Analysis Plan
Version Date: 16-Nov-2020

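### SAP 7.2 defines negative AIA by the screening assay alone, so, read literally, some newly confirmed positive subjects are scored as non-events in the primary analysis

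*SAP*

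**What the plan says.** All of this is in SAP 7.2 unless stated.

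- **Lead paragraph.** A sample below the screening threshold is reported negative. Samples that screen positive "will be subsequently tested in the confirmatory assay and will be reported as either 'negative' or 'confirmed positive". So there are two routes to a negative report. Titres are run only on confirmed samples: "if found to be 'confirmed positive', samples will then undergo AIA titer analysis".
- **Definition 1** requires both assays to be positive for confirmed positive AIA.
- **Definition 2** gives one route to negative: "A subject is deemed to have negative AIA at a time point if the screening assay at that time point has a negative result".
- **Definitions 3 and 4** both build on that term. Definition 3 asks for "negative AIA at baseline and a confirmed positive AIA after baseline and up to visit Week 26" together with neutralizing antibodies; definition 4 sets the same two AIA conditions for newly confirmed positive AIA.
- **Definition 5** (important titre increase) requires a confirmed positive baseline and a baseline titre.
- **Definition 6**, the primary endpoint, is either "Newly Confirmed post-baseline positive AIA (in baseline negative") or the titre increase of definition 5.
- **SAP 11.6.2.1** analyses subjects "with negative AIA at baseline who develop newly confirmed positive AIA after baseline and up to visit Week 26 will be summarized in proportions".
- **SAP Table 4, category 1** applies no imputation when it finds "All three AIA samples collected and analyzed".

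Protocol 8.7.1 counts newly confirmed positive AIA development and does not define negative.

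**The concern.** A baseline sample that screens positive and is not confirmed is negative in the lead paragraph. Under the numbered definitions it is neither negative nor confirmed positive. The primary endpoint is built on the numbered definitions.

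A subject unconfirmed at baseline and confirmed later has newly confirmed AIA in the protocol's sense. The literal SAP rule would not count that event. This is an equivalence trial whose margin is read from the observed Lantus rate, so uncounted events change both the estimated difference and the margin it is compared with.

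**Working it through.** **1. Baseline states against the definitions**

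| Baseline sample | Negative, definition 2 | Negative, lead paragraph | Confirmed positive, definition 1 | Can become a primary event: literal / lead paragraph |
|---|---|---|---|---|
| Screen negative | yes | yes | no | yes / yes |
| Screen positive, not confirmed | no | yes | no | **no / yes** |
| Screen positive, confirmed | no | no | yes | yes / yes |

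In the middle row the first limb of definition 6 fails because the subject is not baseline negative. The second fails because the baseline is not confirmed positive and so has no titre.

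**2. Does another rule repair it?** Table 4 category 1 leaves complete data as they are. Category 4 treats unscheduled positives like the scheduled ones when a baseline result exists. The five sensitivity analyses in 11.6.1.3 do not change the baseline classification. Nothing reclassifies this subject. A subject missing Week 12 or Week 26 is an event under category 2 in any case, so only subjects with complete post-baseline samples are affected.

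**3. The plan's own power figure.** Inputs from SAP 5.1: 275 per arm, 30% in both arms, margin 12%, one-sided 5% tests.

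SE = sqrt(2 × 0.30 × 0.70 / 275) = 0.0391. Power = 2 × Phi(0.12/0.0391 − 1.645) − 1 = 2 × Phi(1.426) − 1 = 84.6%, against the stated 85% or so. It reproduces.

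**4. Illustration.** Let q be the share of subjects with a screen-positive, unconfirmed baseline. It is not in the documents; 2, 5 and 10% are assumptions. Assume also the same q and the same seroconversion for affected and other subjects in each arm, complete samples, and true rates of 42% (test) and 30% (Lantus), which puts the difference exactly on the 12-point margin.

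- Recorded rate = p(1 − q).
- Affected subjects per arm = 275q; events lost = 275qp.
- Margin by linear interpolation in SAP Table 3 = 11.3 + 0.7 × (Lantus rate − 25)/5, which is 11.92, 11.79 and 11.58 points for q = 2, 5 and 10%.
- P(declare equivalence) = Phi((m − d)/SE − 1.645) − Phi((−m − d)/SE + 1.645) with the margin m at the expected Lantus rate. The SAP sets the margin at the observed Lantus rate, so the same probability was also found by enumerating both binomials.

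| q | Affected per arm | Events lost, test / Lantus | Recorded rates, test / Lantus | False equivalence, margin at expected rate | False equivalence, margin at observed rate | Power, 30% vs 30% (formula) |
|---|---|---|---|---|---|---|
| 0 | 0 | 0 / 0 | 42.0 / 30.0% | 5.0% | 5.8% | 84.6% |
| 2% | 5.5 | 2.3 / 1.7 | 41.2 / 29.4% | 5.4% | 6.3% | 84.5% |
| 5% | 13.8 | 5.8 / 4.1 | 39.9 / 28.5% | 6.1% | 7.2% | 84.4% |
| 10% | 27.5 | 11.6 / 8.3 | 37.8 / 27.0% | 7.4% | 8.6% | 84.3% |

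The 5.8% at q = 0 comes from the floating margin, not from definition 2.

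**5. Chance imbalance.** The baseline sample is drawn at screening, before randomization. If the number affected in an arm is Bin(275, q), the event count is Bin(275, p(1 − q)). The enumeration therefore already averages over every chance split; averaging explicitly at q = 5% returns 7.18%.

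**6. Missing samples.** Suppose a share u of each arm is missing a post-baseline sample and counted as an event, with total rates still 42% and 30%. Events lost fall to 275q(0.42 − u) and 275q(0.30 − u), so the losses above are upper values for each q. The shrinkage of the difference is q × 0.12 whatever u is, so the false-equivalence column is not capped in the same way. With u = 10% (assumed) and q = 5%, recorded rates are 0.10 + 0.32 × 0.95 = 40.4% and 0.10 + 0.20 × 0.95 = 29.0%. The enumeration then gives 7.4% against 7.2%.

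**The case against.** The best defence is that 7.2 answers itself. The lead paragraph makes the reported result binary, definition 1 points back to that description, and definition 2 says if, not only if. SAP 3.1 lists no change to who counts as baseline negative. A programmer working from the laboratory's final call would classify these subjects as intended. This stands as evidence of intent. It does not remove the conflict, because definitions 3, 4 and 6 use the defined term, and the documents do not say whether the laboratory transfer holds tier-level results or only a final call.

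It is also fair that every size above is assumed, and that 42% against 30% is the least favourable case. At the planning case of equal 30% rates, power hardly moves.

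Three stronger readings are tempting and not supported:

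- A reader might infer a further bias from an unequal split of affected subjects between arms. The imbalance can only be by chance, and step 5 shows it is already in the figures.
- A reader might extend the point to Table 4 category 3, where a subject without a baseline sample "will be counted as 'NOT developing a treatment-induced AIA' if both Week 12 and Week 26 results are negative". That rule speaks of sample results, which is the lead paragraph's language, and no misclassification follows.
- A reader might extend it to 11.6.2.4. Its body does not restate a baseline-negative condition, so no consequence is shown there.

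**Conclusion.** The point holds as a wording error of low severity. Definition 2 is narrower than the SAP's own testing algorithm. Applied literally, it scores as a non-event a subject who is unconfirmed at baseline, has complete samples and is confirmed later, and it removes that subject from the 11.6.2.1 subset and from definition 3.

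The real size is unknown because q is unknown; if q is zero, nothing changes. Under the assumptions in step 4, false equivalence at the margin rises by 0.5, 1.4 and 2.8 points for q = 2, 5 and 10% (6.3 − 5.8, 7.2 − 5.8, 8.6 − 5.8). Power at 30% in both arms changes by less than half a point.

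A reader might infer that the primary result will be wrong, or biased toward equivalence in general. The documents support neither: they do not show that the literal rule would be programmed, and the direction of the effect depends on the assumptions of equal q and equal seroconversion.

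**What to change.** Before database lock and unblinding, reword definition 2 along these lines: *negative AIA if the screening assay is negative, or the screening assay is positive and the confirmatory assay is negative*. Use that meaning in definitions 3, 4 and 6 and in the 11.6.2.1 subset.

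If tier-level results are in the laboratory transfer, also report the number of screen-positive, unconfirmed baseline samples per arm in the final analysis. That shows whether the issue mattered.

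The cost is one sentence in the SAP and a check of the derivation. It restates the SAP's own algorithm and needs no new samples or assays. SAP section 3 already foresees a final version before database lock. The per-arm count costs one extra table line if the tier-level data are held, and should not be promised if they are not.

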### **8.7.3 Other Secondary Endpoints**

#### **8.7.3.1 Immunogenicity**

- The percentage of subjects in each treatment group with negative AIA at baseline who develop confirmed positive AIA after baseline and up to visit Week 26
- The percentage of subjects in each treatment group with confirmed positive AIA at baseline and at least a 4-fold increase in titers after baseline and up to visit Week 26
- The mean change from baseline in each treatment group in AIA titers after baseline and up to visit Week 26
- The percentage of subjects in each treatment group with confirmed positive AIA after baseline and up to visit Week 26 who develop any anti-insulin neutralizing antibodies after baseline and up to visit Week 26
- The percentage of subjects in each treatment group with confirmed positive AIA after baseline and up to visit Week 26

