#### **12.9.1.4 Subjects with Confirmed Anti-Insulin Antibodies Who Develop Anti-Insulin Neutralizing Antibodies**

The percentage of subjects in each treatment group with confirmed positive AIA after baseline and up to visit Week 26 who develop any anti-insulin neutralizing antibodies after baseline and up to visit Week 26 will be compared using an exact test of difference in proportions.

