11.6.2.3 Change in Anti-Insulin Antibody Titer

The change from baseline in AIA titers at visit Week 12 and visit Week 26 will be summarized descriptively in subjects with confirmed positive AIA at baseline. Though not specified in the protocol, this analysis is planned for the subset of subjects with confirmed positive AIA only.

11.6.2.4 Subjects with Confirmed Positive Anti-Insulin Antibodies Who Develop Newly Confirmed Neutralizing AIA

The percentage of subjects in each treatment group with confirmed neutralizing AIA after baseline and up to visit Week 26 will be compared using difference in proportions. The difference in proportions will be estimated along with the corresponding 90% CI in the SS using a logistic regression model with treatment as the only independent variable in the model.

Missing data will not be imputed, the percentages will be based on the subjects with documented confirmed positive AIA after baseline and up to visit Week 26.

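### The SAP gives two different numerators for the secondary neutralizing antibody endpoint, and one of them does not fit the stated denominator

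*SAP*

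**What the plan says.** **Definition.** SAP 7.2, definition 3, opens: "A subject is deemed to have developed newly confirmed NAb if the subject has a negative AIA at baseline". It then also requires a confirmed positive AIA and a neutralizing antibody after baseline.

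**Heading of the analysis.** SAP 11.6.2.4 is titled "Subjects with Confirmed Positive Anti-Insulin Antibodies Who Develop Newly Confirmed Neutralizing AIA". It is the only analysis in the SAP that uses wording close to the defined term.

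**Body of the analysis.** The sentence under that heading reads: "The percentage of subjects in each treatment group with confirmed neutralizing AIA after baseline and up to visit Week 26 will be compared". The word newly is absent, and so is any condition on baseline AIA.

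**Denominator.** The same section does not impute missing data and states that "the percentages will be based on the subjects with documented confirmed positive AIA after baseline and up to visit Week 26". There is no restriction to subjects negative at baseline.

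**Endpoint.** Protocol 8.7.3.1 takes subjects confirmed positive after baseline and counts those "who develop any anti-insulin neutralizing antibodies after baseline and up to visit Week 26". SAP 6.3.1 repeats this. Protocol 12.9.1.4 carries it into the analysis: subjects "who develop any anti-insulin neutralizing antibodies after baseline and up to visit Week 26 will be compared using an exact test". SAP 3.1, which lists changes from the protocol, mentions no narrowing of this endpoint.

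**Baseline-positive subjects.** SAP 7.2 allows for them: "A subject can have a confirmed positive AIA at any timepoint, including baseline". It also says that "the confirmed positive samples will be tested for neutralizing activity within the neutralizing assay", and it does not exempt baseline samples.

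**The concern.** A proportion is interpretable only when everyone in the denominator could have been counted in the numerator. Definition 3 over the 11.6.2.4 denominator breaks that rule. A subject who is AIA-positive at entry and again after baseline adds one to the denominator and can never add to the numerator, even if the antibodies become neutralizing on study treatment. The protocol endpoint would count that subject.

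Such subjects are foreseeable. Insulin-treated patients are eligible. Exclusion 10 removes only those with antibodies documented in the past, and no criterion excludes a positive AIA result at screening. Both the four-fold titer endpoint and one arm of the primary endpoint definition presuppose baseline-positive subjects.

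The reported NAb percentage in each arm is at stake, and so is the difference between arms. Two programmers reading the same section could produce different tables.

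**Working it through.** The documents give no expected rate, margin or power for the NAb endpoint, so there is no plan figure to reproduce. The check sets the texts side by side, then uses algebra.

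**Step 1. Which text uses which numerator**

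| Source | Event | Requires negative AIA at baseline? |
|---|---|---|
| SAP 7.2, definition 3 | Newly confirmed NAb | Yes |
| SAP 11.6.2.4, heading | Newly confirmed neutralizing AIA | By implication |
| SAP 11.6.2.4, body | Confirmed neutralizing AIA after baseline | No |
| SAP 6.3.1 | Any NAb after baseline | No |
| Protocol 8.7.3.1 and 12.9.1.4 | Any NAb after baseline | No |

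The denominator is the same in 11.6.2.4, 6.3.1 and the protocol: subjects confirmed AIA-positive after baseline.

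**Step 2. Algebra.** Among subjects in that denominator, let b be the share who were AIA-positive at baseline. Let rn and rp be the NAb risks after baseline in those negative and positive at baseline.

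- Definition 3 over the stated denominator: (1-b)*rn
- Endpoint as worded, same denominator: (1-b)*rn + b*rp
- Definition 3 over baseline-negative subjects only: rn

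The first falls short of the second by b*rp. It can never exceed it, and the two agree only if no baseline-positive subject has NAb after baseline. The first falls short of the third by b*rn.

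**Step 3. Illustration.** All values of b, rn and rp below are assumed.

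| b | rn | rp | Definition 3, stated denominator | Endpoint as worded |
|---|---|---|---|---|
| 10% | 20% | 20% | 0.9 × 20% = 18% | 20% |
| 30% | 20% | 20% | 0.7 × 20% = 14% | 20% |
| 50% | 20% | 20% | 0.5 × 20% = 10% | 20% |
| 70% | 20% | 20% | 0.3 × 20% = 6% | 20% |
| 30% | 10% | 0% | 0.7 × 10% = 7% | 7% |
| 30% | 10% | 5% | 7% | 7% + 0.3 × 5% = 8.5% |
| 30% | 10% | 20% | 7% | 7% + 0.3 × 20% = 13% |

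In counts: take 100 subjects positive after baseline, 60 of them baseline-negative with 12 NAb and 40 baseline-positive with 8 NAb. Definition 3 over the stated denominator gives 12/100 = 12%. Any NAb gives (12 + 8)/100 = 20%. Definition 3 over baseline-negatives gives 12/60 = 20%.

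**Step 4. Difference between arms, under definition 3**

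- Equal b, and equal risk by baseline status within each arm: a true difference shrinks by the factor (1-b). At b = 40%, 10 points reads as 0.6 × 10 = 6.
- Unequal b: with a risk of 20% everywhere and b = 30% against 50%, the arms read 0.7 × 20% = 14% and 0.5 × 20% = 10%. That is a 4-point difference where none exists.

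Unequal b is possible. SAP 5.2 randomizes without stratification. The denominator is also formed after randomization, so b depends on how many baseline-negative subjects become positive in each arm.

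**The case against.** A reader might infer that the NAb rate is understated in both arms as a matter of fact. The documents do not support that, for these reasons.

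- The sentence in 11.6.2.4 that says what will be compared has no baseline condition. Taken with the stated denominator, it reproduces the protocol endpoint, and nothing is understated.
- The link to definition 3 is inferred from the heading. The heading's wording differs slightly from the defined term, and 11.6.2.4 does not refer to Section 7.2. The primary analysis and 11.6.2.2 both do so expressly.
- The table shells, which might settle the numerator, are in a separate document not available here.
- The documents do not say how many subjects were AIA-positive at entry. Insulin-naïve subjects are also eligible, and those with previously documented antibodies are excluded, so b could be small.

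All of this stands, and it limits the point to an inconsistency with a conditional consequence. It does not remove the inconsistency. Definition 3 has no other evident use in the SAP, the heading points to it, and nothing says which text governs.

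A reader might also want the denominator to drop subjects already NAb-positive at baseline. That would be a further version of the endpoint: the protocol denominator is everyone confirmed AIA-positive after baseline. It is reasonable as a supportive analysis, but not as the correction.

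The stakes are also limited. This is one of the other secondary endpoints, with no stated margin, and the hierarchy in SAP 11.6.1.4 names only immunogenicity equivalence and efficacy.

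**Conclusion.** The SAP is inconsistent on the numerator of this endpoint and should be corrected. Definition 3 and the heading of 11.6.2.4 exclude baseline-positive subjects from the events. The body of 11.6.2.4, SAP 6.3.1 and the protocol do not.

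The direction of the error, if definition 3 is applied, is certain from arithmetic: the rate is too low by b*rp against the endpoint as worded, and never too high. The size cannot be given. The illustrations rest on assumed values of b, rn and rp. The effect on the difference between arms can go either way when b differs by arm. Whether any understatement occurs depends on which SAP text the programming follows.

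The primary equivalence test on treatment-induced AIA does not use the NAb definition and is unaffected.

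**What to change.** 1. In SAP 11.6.2.4, define the numerator as any neutralizing antibody after baseline and up to Week 26 among subjects confirmed AIA-positive after baseline, as in the protocol endpoint. Leave the denominator as it is.
2. Remove Newly Confirmed from the heading of 11.6.2.4.
3. If definition 3 is kept, report it only as a labelled additional analysis. Its denominator should be subjects AIA-negative at baseline and confirmed positive after baseline.
4. Optional and supportive: show NAb results split by baseline AIA status, or repeat the analysis excluding subjects already NAb-positive at baseline. SAP 7.2 has all confirmed positive samples tested for neutralizing activity, so the baseline results should exist.

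The cost is an edit to the SAP text and the matching table shell. No new data or samples are needed.
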